## **2.4 Analysis of the key secondary objective**

### **2.4.1 Key secondary endpoint**

The key secondary endpoint was the composite of treated biopsy proven acute rejection (BPAR), graft loss or death at Month 12.

### **2.4.2 Statistical hypothesis, model, and method of analysis**

The incidence of the composite of treated biopsy proven acute rejection (BPAR), graft loss or death until Month 12 was estimated using the Kaplan-Meier method.

The number of events as well as the number of censored observations will be presented. Kaplan-Meier estimates will be presented by quarter up to Month 12. Percentiles (25%, median, 75%) of the event time distribution will be presented together with their two-sided 95% confidence interval. The two groups were compared using the log-rank test. Kaplan-Meier curve was displayed graphically.

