## 6.4 Treatment assignment

At Baseline (Visit 2), which has to take place prior to randomization, all patients who meet the inclusion and do not fulfill any of the exclusion criteria will be given the lowest available number on the randomization list of the respective stratum. This number assigns them to one of the treatment arms. The investigator will enter the randomization number on the CRF.

The randomization numbers will be generated using the following procedure to insure that treatment assignment is unbiased and concealed from patients and investigator staff. A

randomization list will be produced under the responsibility of the Novartis Nürnberg GCP Officer using a validated system that automates the random assignment of treatment arms to randomization numbers in the specified ratio. Randomization will be stratified by HCV status (positive/negative) and lab MELD (Model of End Stage Liver Disease) score below/equal or above 30 at transplantation.

Randomization of individual patients will be performed centrally by a CRO. Allocation of a patient to one of the two treatment groups will be performed in the following steps.

1. Information about patient enrolment (Screening Visit):

Study sites will inform the CRO about each patient inclusion via fax

2. Randomization (Baseline Visit):

At day of randomization, the site will provide the information of eligible patient to the CRO by fax.

The CRO will allocate the patient the next free consecutive randomization number allocated to the site. Randomization number and allocated treatment (according to the randomization list) will be provided to the site by fax.

The randomization number will be entered on the CRF of an individual patient.

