#### Efficacy-related objectives

The incidence of efficacy-related endpoints will be estimated using the Kaplan-Meier method. The number of events as well as the number of censored observations will be presented. Kaplan-Meier estimates will be presented by visit up to Month 12. Percentiles (25%, median, 75%) of the event time distribution will be presented together with their two-sided 95% confidence interval. The two groups will be compared using the log-rank test. Kaplan-Meier curves will be displayed graphically. For rejections, Kaplan-Meier analyses may be stratified by severity grade.

The following endpoints will be analyzed:

- Incidence of a composite of treated biopsy proven acute rejection (BPAR), graft loss or death at Month 12.
- Incidence of a composite of treated BPAR, graft loss, death or loss to follow-up.
- Incidence of a composite of death or graft loss.
- Incidence of acute rejection, treated acute rejection, BPAR, treated BPAR, graft loss, or death

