### **2.3.4 Statistical hypothesis, model, and method of analysis**

The trial tests the null hypothesis that the treatment difference (investigational minus control) in mean eGFR at Month 12 after baseline is zero versus the alternative hypothesis that the treatment difference was different from zero.

The hypotheses was tested with an analysis of covariance (ANCOVA) with treatment , center, HCV-Class (positive, negative) and lab MELD ( $\leq 30$  vs  $> 30$ ) as factors, and eGFR at Visit 2 (Baseline) as covariate. Raw as well as adjusted means (= LS-means, LS: least square means) were presented for the treatment contrast together with a two-sided p value and the appropriate confidence interval, respectively. The significance level was 5% (two-sided). There are no multiplicity issues to be addressed since only the hypothesis of superior efficacy of the investigational vs. the control regimen was tested confirmatorily.

The Full Analysis Set was used for the primary analysis. Patients will be analyzed in their randomized group.

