## **2.5 Analysis of secondary efficacy objective(s)**

### **2.5.1 Secondary endpoints**

The following secondary efficacy variables were analyzed in an explorative manner for the full analysis set (FAS):

- efficacy-related endpoints, such as acute rejection, treated biopsy proven acute rejection (BPAR), graft loss, death and loss to follow-up (as composites or individual endpoints)
- endpoints related to renal function: eGFR using various methods (Nankivell, Cockcroft-Gault, CKD EPI and Hoek formulae

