### **2.5.2 Statistical hypothesis, model, and method of analysis**

#### **Efficacy-related objectives**

The incidence of efficacy-related endpoints was estimated using the Kaplan-Meier method. The number of events as well as the number of censored observations was presented. Kaplan-Meier estimates were presented by quarter up to Month 12. Percentiles (25%, median, 75%) of the event time distribution were presented together with their two-sided 95% confidence interval. The two groups will be compared using the log-rank test. Kaplan-Meier curves were displayed graphically

The number of max. severity by patient was reported by frequency tables.

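### The log-rank tests for the key secondary composite and other efficacy events leave out the HCV and lab MELD randomisation strata: valid, but slightly less sensitive if the strata are prognostic

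*SAP*

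**What the plan says.** - **Design.** Protocol 6.4: "Randomization will be stratified by HCV status (positive/negative) and lab MELD (Model of End Stage Liver Disease) score below/equal or above 30 at transplantation". This gives four strata.
- **Primary model.** SAP 2.3.4 fits an ANCOVA with treatment and "center, HCV-Class (positive, negative) and lab MELD" as factors. The MMRM code in SAP 5.5.2 also carries the HCV and lab MELD classes.
- **Key secondary endpoint** (treated BPAR, graft loss or death). SAP 2.4.2: "The two groups were compared using the log-rank test". No strata are named.
- **Other efficacy endpoints** (the rejection categories, graft loss, death and the other composites). SAP 2.5.2: "The two groups will be compared using the log-rank test". Protocol 10.5.1 is equally silent on strata. The only stratification it mentions is "For rejections, Kaplan-Meier analyses may be stratified by severity grade", and severity is a feature of the outcome, not a design factor.
- **Status.** SAP 2.3.4 says "There are no multiplicity issues to be addressed since only the hypothesis of superior efficacy" is tested as confirmatory. SAP 2.5.1 calls the secondary efficacy variables exploratory, and its list includes the key secondary composite. Protocol 10.8 and SAP 3 say that power for secondary variables was not investigated.
- **Changes.** The statistical changes listed in SAP 4 do not mention the matter.

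The documents never call the log-rank test unstratified. That reading rests on the absence of any strata in all three places.

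**The concern.** The plan adjusts for the stratification factors in the eGFR models but not in the event comparisons, and gives no reason for the difference. Stratified allocation balances the strata between arms by design. If the strata differ in risk, an unstratified log-rank test uses a variance that ignores this balance and is therefore too large. The test then rejects less often than its nominal level under the null, and less often than it could when there is a real difference.

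The direction matters here. The investigational arm runs tacrolimus at a trough below 5 ng/mL against 6-10 ng/mL in control, so any renal gain will be read alongside rejection, graft loss and death. For that comparison, lost sensitivity leans towards a reassuring non-significant result.

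**Working it through.** **The plan's own figure.** The only sample-size figure is for eGFR. A two-sample t-test with difference 7.0, SD 18 and n = 105 per group gives 80.1% power. Inflation gives 105/(1 − 0.20)² = 105/0.64 = 164.06, rounded up to 165 per group, 330 in all. Both reproduce, but neither bears on the log-rank test. No event rate, hazard ratio or stratum risk is given for any event endpoint.

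**Method.** Simulate 330 patients, 1:1, in permuted blocks within the four strata, with exponential event times and follow-up to Month 12. Compute Z = Σ(O − E)/√ΣV, first with all patients in one risk set and then summed over the four strata. Reject if |Z| > 1.96.

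**Set A (assumed values).** 25% HCV-positive; 10% control event risk in the lowest-risk stratum; treatment hazard ratio 1.8 (more events on the investigational arm); 4,000 runs per cell. The ratios multiply the hazard for MELD > 30 and for HCV-positive.

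| MELD > 30 | Ratios MELD / HCV | Power, unstratified | Power, stratified | Gain (points) | Type I error, unstratified |
|---|---|---|---|---|---|
| 20% | 1 / 1 | 47.5% | 47.7% | 0.2 | – |
| 20% | 2 / 1.5 | 57.8% | 58.8% | 1.0 | 4.9% |
| 20% | 3 / 1.5 | 61.6% | 64.2% | 2.6 | 4.0% |
| 20% | 4 / 1.5 | 62.0% | 67.1% | 5.1 | 4.3% |
| 20% | 6 / 2 | 65.7% | 76.8% | 11.1 | 3.2% |
| 10% | 2 / 1.5 | 56.8% | 56.9% | 0.1 | – |
| 10% | 4 / 1.5 | 57.8% | 61.0% | 3.2 | – |
| 10% | 6 / 2 | 59.3% | 67.4% | 8.1 | – |

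Repeat runs gave gains of about 0 to 1 point at 1/1 to 2/1.5, 2 to 4 points at 3/1.5 to 4/1.5, and 7 to 11 points at 6/2. The simulation error of a single power estimate is about √(0.6 × 0.4/4000) = 0.8 point.

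**Set B (assumed values).** 25% HCV-positive, 10% MELD > 30, about 20% censored by Month 12, overall control risk 10% or 20%, treatment hazard ratio 0.5, same prognostic hazard ratio for each factor; 10,000 runs.

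| Control risk (events) | Ratio per factor | Power, unstratified | Power, stratified |
|---|---|---|---|
| 10% (about 22) | 1 | 35.6% | 35.3% |
| 10% | 2 | 34.4% | 34.8% |
| 10% | 3 | 35.1% | 36.3% |
| 20% (about 45) | 1 | 62.5% | 62.5% |
| 20% | 2 | 61.5% | 62.6% |
| 20% | 3 | 59.5% | 62.8% |

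With 50% HCV-positive, 20% MELD > 30, 20% control risk and ratio 3, power goes from 59.6% to 63.2%. Type I error across the set is 4.3-5.1% unstratified and 4.6-5.3% stratified.

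**How extreme is 6/2?** Starting from a 10% control risk, a hazard multiplier of 6 gives 1 − 0.9⁶ = 47% (MELD > 30, HCV-negative), and 6 × 2 = 12 gives 1 − 0.9¹² = 72% (both factors). At a treatment hazard ratio of 1.8 the investigational arm would reach 1 − 0.9^10.8 = 68% and 1 − 0.9^21.6 = 90%. Nothing in the documents supports gradients of that size.

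**Smallest stratum.** With 10% MELD > 30 and 25% HCV-positive, independent of each other, 330 × 0.10 × 0.25 ≈ 8 patients fall in the stratum with both. Even with a stratum that small, stratifying lost no more than about 0.3 point when the factors were not prognostic.

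**The case against.** The planned test is valid: its only defect is conservatism, and only if the strata are prognostic. It also matches the marginal Kaplan-Meier curves and quarterly estimates it accompanies. The analyses are exploratory and no decision rule or margin hangs on the p value. All of this stands, and it limits the point to a minor one.

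Four stronger readings are tempting, and the documents do not support them.

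- **A material loss of power.** A reader might infer this from the 6/2 rows. They need event risks of 47% and 72% in the high-MELD control strata. Under moderate gradients the loss is a point or less.
- **The log-rank result decides whether a renal benefit is acceptable, on an endpoint the sponsor calls unpowered.** No section gives the test that role. The documents say power was not investigated, which is not the same as saying it is inadequate. If the worry is that non-significance will be read as safety, a stratified p value does not cure that.
- **Every time-to-event comparison is affected.** The point covers the listed efficacy endpoints. For time to renal replacement therapy (SAP 1.3) no test is named.
- **Stratifying is free.** The strata are not uniquely defined. HCV is IgG at screening in SAP 1.3.1, but any positive HCV or HCV-IgG result at screening or baseline in SAP 5.5.1. Lab MELD is taken at transplantation in Protocol 6.4 and at screening in SAP 1.3.1. This must be settled before the test can be programmed.

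**Conclusion.** The inconsistency is real: the design and the eGFR models use HCV status and lab MELD, and the log-rank tests for the key secondary composite and the other listed efficacy endpoints do not. The consequence is small. Under the assumed values in set A, stratifying gains about 0-1 point of power for weak to moderate prognosis, about 2-5 points for strong prognosis, and more only under extreme gradients. Set B, with fewer events, gives about 0 to 3.6 points. If the strata are not prognostic, power is essentially unchanged.

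Stratum sizes, event risks and prognostic ratios are all assumptions, so the direction is firmer than the size. Severity is minor: the test is valid and the analyses are exploratory.

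**What to change.** In SAP 2.4.2 and 2.5.2, compare the arms with a log-rank test stratified by HCV status (positive/negative) and lab MELD (≤ 30 vs > 30), using the stratum values recorded at randomisation. Keep the unstratified test as supportive, next to the Kaplan-Meier curves. State one definition of each stratum and reconcile Protocol 6.4, SAP 1.3.1 and SAP 5.5.1 with it.

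The cost is a sentence in each SAP section, a STRATA statement in the program and the work of settling the definitions. No new data are needed if the randomisation values are on file. The downside is that very small strata add little information.

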### **2.4.3 Handling of missing values/censoring/discontinuations**

If no event occurred until Month 12 or End of Study the observation period will be censored at Month 12 (day 360 or at end of study)

## **2.5 Analysis of secondary efficacy objective(s)**

### **2.5.1 Secondary endpoints**

The following secondary efficacy variables were analyzed in an explorative manner for the full analysis set (FAS):

- efficacy-related endpoints, such as acute rejection, treated biopsy proven acute rejection (BPAR), graft loss, death and loss to follow-up (as composites or individual endpoints)
- endpoints related to renal function: eGFR using various methods (Nankivell, Cockcroft-Gault, CKD EPI and Hoek formulae

#### **Efficacy-related objectives**

The following endpoints until Month 12 were analyzed:

- acute rejection,
- treated acute rejection,
- BPAR,
- treated BPAR,
- graft loss,

- death
- composite of treated biopsy proven acute rejection (BPAR), graft loss or death.
- composite of treated BPAR, graft loss, death or loss to follow-up
- composite of graft loss or death.

### **Renal function-related objectives**

Renal function as assessed by eGFR calculated according to the CKD-EPI, Cockcroft-Gault, Nankivell, and Hoek formulas were the further renal function-related secondary parameter. Further parameter was the proteinuria.

### **2.5.2 Statistical hypothesis, model, and method of analysis**

#### **Efficacy-related objectives**

The incidence of efficacy-related endpoints was estimated using the Kaplan-Meier method. The number of events as well as the number of censored observations was presented. Kaplan-Meier estimates were presented by quarter up to Month 12. Percentiles (25%, median, 75%) of the event time distribution were presented together with their two-sided 95% confidence interval. The two groups will be compared using the log-rank test. Kaplan-Meier curves were displayed graphically

The number of max. severity by patient was reported by frequency tables.

#### **Renal function-related objectives**

Renal function were analyzed using the ANCOVA model specified for the primary analysis. Raw as well as adjusted means were presented for the treatment contrast together with its confidence interval and two-sided exploratory p values separately for each time point.

Additionally to the analysis at Month 12, an analysis at Month 6 (included eGFR calculated by MDRD-4 formula) was performed.

The incidence of proteinuria was analyzed using frequency tables by-treatment group as adverse of special interest.

### **2.5.3 Handling of missing values/censoring/discontinuations**

Missing values will be dealt with in the ANCOVA analysis by LOCF-method.

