#### Renal function-related objectives

Renal function as assessed by cGFR calculated according to the CKD-EPI, Cockcroft-Gault, Nankivell, MDRD-4, and Hoek formulas (see [Section 7.5](#)) will be analyzed using the ANCOVA model specified for the primary analysis. Raw as well as adjusted means will be presented for the treatment contrast together with its confidence interval and two-sided exploratory  $p$  values separately for each time point. Missing values will be dealt with in the ANCOVA analysis by multiple imputation. Additionally to the analysis at Month 12, an analysis at Month 6 will be performed.

Descriptive statistics for observed values and changes from baseline as well as within-group and between-group comparisons using suitable parametric and non-parametric statistical tests will be displayed by visit and treatment group. Additionally, descriptive statistics will be presented for the following subgroups:

- age: <60 vs.  $\geq$ 60 years
- gender: male vs. female
- renal function at baseline: 30 – <45, 45 – <60,  $\geq$ 60 mL/min/1.73m^2; <45 vs  $\geq$ 45 mL/min/1.73m^2, <60 vs.  $\geq$ 60 mL/min/1.73m^2
- HCV status at baseline: positive vs. negative

- lab MELD score at baseline:  $\leq 14$ ,  $15 - 19$ ,  $20 - 24$ ,  $25 - 29$ ,  $\geq 30$

Serum creatinine as well as the urinary protein/creatinine ratio will be summarized using descriptive statistics for observed values and changes from baseline. Within-group and between-group comparisons will be performed using suitable parametric and non-parametric statistical tests and will be displayed by visit and treatment group.

The incidence of patients experiencing a decline in eGFR of  $<10$ ,  $10 - <15$ ,  $15 - <20$ ,  $20 - <25$ , and  $\geq 25$  mL/min/1.73m^2 from baseline will be analyzed using frequency tables by visit and treatment group. Treatment groups will be compared exploratory using the Pearson's Chi-Square test (where all expected numbers are at least 1), otherwise Fisher's exact test will be used.

The incidence of proteinuria of  $0.5 - <1.0$  g/day,  $1.0 - <3.0$  g/day and  $\geq 3.0$  g/day will be analyzed using frequency tables by visit and treatment group. Treatment groups will be compared exploratory using the Pearson's Chi-Square test (where all expected numbers are at least 1), otherwise Fisher's exact test will be used.

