### **2.3.5 Handling of missing values/censoring/discontinuations**

Missing values in eGFR will be imputed with the last valid observed value from that patient (LOCF). Under the assumption that the eGFR will remain fairly stable in the control group but will probably improve in the investigational group, this strategy corresponds to a conservative estimate of the treatment effect.

As sensitivity analyses a multiple imputation (Molenberghs & Kenward 2007; White, Royston & Wood 2010) will be performed. The specification for the multiple imputation procedure are presented in appendix 5.5.2.

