**Changes in statistical methods in comparison to the protocol:**

The Virus (HCV, CMV) and Hepatocellular Carcinoma (HCC) related secondary objective “• To evaluate rates of progression of HCV related allograft fibrosis are deleted. Reason is, that the in case from HCV the biopsies were not performed adequately.

The incidence of proteinuria of  $0.5 - <1.0$  g/day,  $1.0 - <3.0$  g/day and  $\geq 3.0$  g/day could not be analysed, because in urine analysis protein is measured in g/l and not in g/day. Therefore, proteinuria could be only documented as adverse event. Therefore proteinuria is defined as further adverse event of special interest.

CNV viral infection were defined as further adverse event of special interest.

Treatment emergent events were defined as all adverse started at baseline or later.

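### The SAP uses LOCF for the secondary eGFR ANCOVAs where the protocol specifies multiple imputation, and its list of changes does not record the switch

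*SAP*

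**What the plan says.** Protocol 10.5.1, under the renal function objectives, applies the primary ANCOVA model to eGFR by CKD-EPI, Cockcroft-Gault, Nankivell, MDRD-4 and Hoek, at Month 12 and also at Month 6. It then states: "Missing values will be dealt with in the ANCOVA analysis by multiple imputation". No drop-out threshold or other condition is attached.

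SAP 2.5.1 names the secondary variables as "Renal function as assessed by eGFR calculated according to the CKD-EPI, Cockcroft-Gault, Nankivell, and Hoek formulas", and SAP 2.5.2 says "Renal function were analyzed using the ANCOVA model specified for the primary analysis". SAP 2.5.2 also adds a Month 6 analysis that includes MDRD-4. For missing data in these ANCOVAs, SAP 2.5.3 states: "Missing values will be dealt with in the ANCOVA analysis by LOCF-method".

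SAP Section 4 has a list headed "Changes in statistical methods in comparison to the protocol". Its items are the dropped HCV fibrosis progression objective, the handling of proteinuria, CMV infection as an event of special interest, and the definition of treatment-emergent events. None concerns missing data.

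For the primary endpoint, SAP 2.3.5 and 5.2 also use LOCF.

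**The concern.** The two documents give different rules for the same analyses, and the list that should record the difference is silent. A reader who relies on Section 4 would believe that the secondary eGFR results come from multiple imputation.

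The methods differ in substance. LOCF is single imputation: it treats the carried-forward value as if it had been observed at the target visit and adds no uncertainty for having filled it in. SAP 2.3.5 calls LOCF conservative only "Under the assumption that the eGFR will remain fairly stable in the control group but will probably improve in the investigational group". The protocol's background section links long-term calcineurin inhibitor use to chronic renal dysfunction, so a stable control arm is an assumption and not a given.

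The primary endpoint has an MMRM beside its LOCF analysis. The SAP text specifies nothing of the kind for the four alternative formulas, so their results could not show whether they depend on LOCF.

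**Working it through.** **1. The rules side by side**

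| Analysis | Protocol | SAP | Other missing-data analysis in the SAP text |
|---|---|---|---|
| Four alternative formulas, Month 12 | Multiple imputation (10.5.1) | LOCF (2.5.3) | None |
| Four alternative formulas, Month 6 | Multiple imputation (10.5.1) | LOCF (2.5.3) | None |
| MDRD-4, Month 6 | Multiple imputation (10.5.1) | LOCF (2.5.2 with 2.5.3) | No multiple imputation; the MMRM contrast is to be presented for Month 12 |
| MDRD-4, Month 12 (primary) | LOCF (10.4.3), but also within the formulas listed in 10.5.1 | LOCF (2.3.5, 5.2) | MMRM; multiple imputation stated both ways |

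The first three rows are plain departures from the protocol. In the fourth the protocol disagrees with itself.

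**2. Does another provision permit the switch?** Protocol 10.4.4 makes multiple imputation conditional on drop-out above 20% or on relevant differences in drop-out pattern between the arms. That condition sits among the supportive analyses of the primary endpoint; 10.5.1 does not repeat or refer to it. SAP 2.3.6 cites fewer than 20% discontinuations as the reason for no multiple imputation, but again for the primary endpoint. It gives no split by arm and does not address the second trigger.

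**3. Was multiple imputation run anyway?** SAP 2.3.5 says it will be done as a sensitivity analysis, SAP 2.3.6 says it was not done, and the note to file says it was programmed and reported. The note names no endpoints, so the method behind the reported secondary results cannot be settled from the documents.

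**4. Figures in the plan.** No stated figure rests on this point. The sample size reproduces: with a difference of 7.0 and an SD of 18.0, the two-sample t-test has 80.1% power at 105 per group, and 105/(1 - 0.20)² = 164.06, rounded up to 165. Neither number changes with the missing-data method of the secondary analyses.

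**5. Illustration of LOCF bias (assumed inputs).** The documents give no missingness by arm and no eGFR trajectory. Let D be the true difference at the target visit, c the control-arm change that occurs after the last observed value, and d_E and d_C the shares missing on everolimus and control. Assume that the carried-forward values pre-date any change, so the unseen change is c on control and c + D on everolimus. Then

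LOCF estimate = D - d_E(c + D) + d_C·c, and bias = -d_E(c + D) + d_C·c.

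With d_E = 0.20 and d_C = 0.10, in mL/min/1.73m²:

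- D = 0, c = -5: -0.20(-5) + 0.10(-5) = +0.5
- D = 0, c = -10: -0.20(-10) + 0.10(-10) = +1.0
- D = 0, c = +10: -0.20(10) + 0.10(10) = -1.0
- D = 7, c = -5: -0.20(2) + 0.10(-5) = -0.9
- D = 7, c = -10: -0.20(-3) + 0.10(-10) = -0.4

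With D = 7 and 20% missing in both arms, c cancels: the bias is -0.20 × 7 = -1.4, and the estimate is 5.6.

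The sign therefore depends on D, on c and on which arm has more missing data. In these cases the absolute bias is 0.4 to 1.4, which is 0.4/18 = 0.02 to 1.4/18 = 0.08 of the planned SD.

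**The case against.** There is a good case that this matters little. The secondary variables are declared exploratory in both documents, and the only confirmatory test is the primary one. Using LOCF throughout while changing only the formula isolates the effect of the formula. The primary endpoint has an MMRM and a per-protocol repeat.

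The protocol's own position is also untidy. Section 10.4.3 ends with a stray fragment about multiple imputation after the LOCF rule, and 10.4.4 makes the method conditional for the primary. The sentence in 10.5.1 could be a leftover.

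Most of this stands as a limit on weight. It does not remove the departure: 10.5.1 is current text, it is unconditional, and the SAP neither follows it nor records leaving it.

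Three stronger readings are tempting, and the documents do not support them:

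- **That these analyses were meant as robustness checks and now fail together with the primary.** The stated objective is only to evaluate renal function by several methods; no robustness role is given.
- **That patients who stop everolimus become missing and are frozen at an early value.** Protocol 6.6.3 and 6.6.8 require Month 12 assessments for all randomized patients, and Section 7 keeps the GFR calculation mandatory at Visit 9 after discontinuation. Under SAP 5.2, LOCF carries the last available value up to Month 12, including Visit 9a, which may be a late one.
- **That LOCF favours everolimus.** At a true difference of 7, the assumed inputs with 20% against 10% missing and a control-arm fall give a bias against everolimus.

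**Conclusion.** The point holds as an unrecorded departure from the protocol. The SAP replaces the specified multiple imputation with single imputation for the four alternative formulas at Months 6 and 12 and for MDRD-4 at Month 6, and Section 4 does not say so. The primary endpoint's 20% drop-out condition does not cover these analyses.

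The confirmatory test and the sample size are untouched. The size and direction of any bias cannot be obtained from the documents, and it may favour either arm; the illustrative values rest wholly on assumed missingness and trajectories. SAP 2.3.6 reports fewer than 20% study discontinuations, which limits the likely effect, although no split by arm is given. A correction is worth making because the protocol's method adds the missing uncertainty and the change is cheap.

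**What to change.** - Apply the protocol's multiple imputation to the secondary eGFR ANCOVAs: the four alternative formulas at Months 6 and 12, and MDRD-4 at Month 6. Keep LOCF as the sensitivity version.
- In SAP Section 4, list any departure that remains, with its reason. State which endpoints the multiple imputation mentioned in the note to file covered.
- For MDRD-4 at Month 12, reconcile protocol 10.5.1 (multiple imputation) with the LOCF rule in protocol 10.4.3 and SAP 2.3.5.
- Correct the SAP 5.5.2 code before re-use. Center is in the CLASS statement but missing from the model statement, although SAP 2.3.4 includes it as a factor. The Estimates output goes to gfr_imp, while MIANALYZE reads LSMeanDiff, which no shown step creates; write the output to LSMeanDiff.

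The cost is a modest amount of programming, some SAP wording, and two sets of secondary eGFR results to report. No further patients or data are needed.
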